## **17.2 Clinical Study Report**

A final clinical study report (CSR) will be prepared according to the ICH guideline on structure and contents of CSRs. The final CSR will include data on any subject that has signed the informed consent, regardless of whether the study is completed or prematurely terminated. Where appropriate, an abbreviated report may be prepared. The CSR will comply with any applicable regulatory requirements, national laws in force and will be in English.

An analysis will be performed on the final response data 12 months after the last subject received the first cabozantinib administration. This analysis will be included in the final study report. An addendum to the report, including the analysis of data from the follow-up period, will be prepared 18 months after the last subject received the first cabozantinib administration.

**19 LIST OF APPENDICES**

Appendix 1 Memorial Sloan Kettering Cancer Center (MSKCC) Criteria for prognostic risk category.....	95
Appendix 2 International Metastatic RCC Database Consortium (IMDC) risk group category .....	97
Appendix 3 Methods of contraception .....	99
Appendix 4 Warnings, Precautions and Guidelines for The Management of Potential Cabozantinib Adverse Events.....	101
Appendix 5 Response Evaluation Criteria in Solid Tumours (RECIST) 1.1 .....	114
Appendix 6 FKSI-DRS Questionnaire .....	122
Appendix 7 Performance Status Criteria .....	124
Appendix 8 Amendment Form #1 .....	126
Appendix 9 Amendment Form #2 .....	166
Appendix 10 Amendment Form #3 .....	170

**Appendix 1 Memorial Sloan Kettering Cancer Center (MSKCC) Criteria for  
prognostic risk category**

The identified prognostic factors include:

- Low Karnofsky performance status (<80%)
- Low serum haemoglobin (<13 g/dL for males and ≤11.5 g/dL for females)
- High corrected calcium (≥10 mg/dL)

Number of risk factors	Risk category
0	Favourable
1	Intermediate
2 or 3	Poor

**Appendix 2 International Metastatic RCC Database Consortium (IMDC) risk group category**

**Risk factors**

- Karnofsky performance status <80%
- Haemoglobin <lower limit of normal (<LLN)
- Time from diagnosis to treatment of <1 year
- Corrected calcium above the upper limit of normal (>ULN)
- Platelets greater than the upper limit of normal (>ULN)
- Neutrophils greater than the upper limit of normal (>ULN)

Number of risk factors	Risk category
0	Favourable
1–2	Intermediate
3+	Poor

**Appendix 3 Methods of contraception**

Female subjects of childbearing potential (i.e. less than or equal to 2 years post-menopause and not surgically sterile) and their partners must agree to use highly effective methods of contraception (that alone or in combination result in a failure rate of less than 1% per year when used consistently and correctly) during the course of the study and for 4 months after the last dose of study treatment.

The interaction of cabozantinib with oral contraceptives has not been investigated and the contraceptive effect may not be guaranteed, therefore it is recommended that an additional contraceptive method such as a barrier method (e.g. condom or diaphragm) is used by your patient if they are using oral combined contraception or progestogen-only contraception.

Effective methods of birth control include:

- Hormonal contraception (oral, injectable, implantable, transdermal) plus a barrier method;
- intrauterine device (IUD) or intrauterine hormone-releasing system (IUS) plus a barrier method;
- bilateral tubal occlusion (females);
- vasectomized partner (males).

Men with partners who can get pregnant will need to use one of the medically accepted methods of birth control listed above while in this study, as will their partner. All male subjects must refrain from donating sperm and sexual intercourse without condoms with female partners for the duration of study and for 120 days after the last dose of study drug.

**Appendix 4 Warnings, Precautions and Guidelines for The Management of Potential  
Cabozantinib Adverse Events**

## 1 GASTROINTESTINAL DISORDERS

### Gastrointestinal perforation, GI fistula, and intra-abdominal and pelvic abscess

Prior to initiation of treatment with cabozantinib, subjects should be carefully evaluated for potential risk factors including (but not limited to) the following:

- Tumours invading GI or respiratory tracts
- Active peptic ulcer disease, inflammatory bowel disease (e.g., ulcerative colitis, Crohn's disease), diverticulitis, cholecystitis or symptomatic cholangitis, or appendicitis
- History of abdominal fistula, GI perforation, bowel obstruction, or intra-abdominal abscess
- Ongoing visceral complications from prior radiation therapy
- Prior GI surgery (particularly when associated with delayed or incomplete healing)

Complete healing following abdominal surgery and radiation therapy and/or resolution of intra-abdominal abscess must be confirmed prior to initiating treatment with cabozantinib.

After starting cabozantinib, subjects should be monitored for early signs of GI perforation such as abdominal pain, nausea, emesis, constipation, and fever especially if known risk factors for developing GI perforation or fistula are present.

Discontinue cabozantinib and initiate appropriate management in subjects who have been diagnosed with GI perforation or fistula.

### Diarrhoea

Subjects should be instructed to notify their physician immediately at the first signs of poorly formed or loose stool or an increased frequency of bowel movements. Guidelines for the evaluation and management of diarrhoea are shown in [Table A1.1](#) .

Table A1. 1 Guidelines for Management of Treatment-Emergent Diarrhoea

Status	Management
Tolerable Grade 1-2 (duration <48 hours)	
 
• Continue with study treatment and consider dose reduction
 
• Initiate treatment with an antidiarrheal agent (e.g. loperamide 4 mg followed by 2 mg after each episode of diarrhoea [maximum: 16 mg loperamide per day])
 
• Dietary modifications (e.g. small lactose-free meals, bananas and rice)
 
• Intake of isotonic fluids (1-1.5 L/day)
 
• Re-assess after 24 hours: 
 
- Diarrhoea resolving to baseline bowel habits: gradually add solid foods and discontinue or decrease antidiarrheal treatment after 12 hours diarrhoea-free interval
 
- Diarrhoea not resolving: Continue/resume antidiarrheal treatment
 
 
 

Intolerable Grade 2, Grade 2 >48 hours, or $\geq$ Grade 3	
 
• Interrupt study treatment
 
• Ask subject to attend investigational site
 
• Rule out infection (e.g. stool sample for culture) 
 
- Administer antibiotics as needed (e.g. if fever or Grade 3-4 neutropenia persists >24 hours)
 
 
 
• Administer fluids (1-1.5 L/day oral or intravenous (IV), as appropriate) for hydration or to correct electrolyte abnormalities
 
• For Grade 3-4 or complicated lower grade diarrhoea consider hospitalisation and IV hydration
 
• Re-assess after 24 hours 
 
- Diarrhoea resolving to baseline bowel habits or Grade <math>\leq</math>1: consider restarting study treatment at reduced dose
 
- Diarrhoea not resolving: 
 
- Start and or continue antidiarrheal treatment (e.g. loperamide 4 mg followed by 2 mg after each episode of diarrhoea (maximum: 16 mg loperamide per day))
 
- Consider starting 2nd line antidiarrheal or referral to gastroenterologist
 
 
 
 
 

Administration of antidiarrheal/antimotility agents is recommended at the first sign of diarrhoea as initial management. Some subjects may require concomitant treatment with more than one antidiarrheal agent. When therapy with antidiarrheal agents does not control the diarrhoea to tolerable levels, study treatment should be temporarily interrupted, or dose reduced. When the diarrhoea is controlled, retreatment with cabozantinib may be acceptable per Investigator decision.

In addition, general supportive measures should be implemented such as continuous oral isotonic hydration, correction of fluid and electrolyte abnormalities, small frequent meals, and stopping lactose-containing products, high-fat meals, and alcohol.

Recurrent or prolonged diarrhoea can be associated with anal or perianal skin erosions which increase the risk for anal abscesses, fistulas, or proctitis. Good personal hygiene should be emphasised. Regular examinations of the perianal region should be performed whenever

diarrhoea has occurred during treatment with cabozantinib. Infections of the perianal region should be treated per local guidelines.

#### Nausea and Vomiting

Antiemetic agents are recommended as clinically appropriate for treatment or prophylaxis of nausea and vomiting, along with supportive care. Dehydration and electrolyte abnormalities may be associated with vomiting and monitoring for and correction of fluid and electrolyte disturbances should be implemented. Antiemetic medications should be assessed for potential drug interactions.

## **2 NON-GASTROINTESTINAL FISTULA**

Non-GI fistula formation: Complications from radiation therapy has been identified as a possible predisposing risk factor for fistula formation in subjects undergoing treatment with cabozantinib.

Subjects with any clinically relevant ongoing complications from prior radiation therapy (i.e. radiation esophagitis or other inflammation of the viscera) should not be treated with cabozantinib.

Radiation therapy to the thoracic cavity (including mediastinum) should be avoided within 3 months of starting treatment with cabozantinib (excluding local radiation for bone metastases). Fistula should be ruled out as appropriate in cases of onset of severe mucositis or difficulty swallowing after start of therapy. Discontinue cabozantinib and initiate appropriate management in subjects who have been diagnosed with a non-GI fistula.

## **3 HAEMORRHAGE**

Haemorrhagic events, including serious and sometimes fatal events, have been reported with cabozantinib. Subjects should be evaluated for potential bleeding risk factors prior to initiating cabozantinib treatment and should be monitored for bleeding events with serial complete blood counts and physical examination while on study. Risk factors for haemorrhagic events may include (but may not be limited to) the following:

- Tumour of the lung with cavitary lesions or tumour lesions which invade or encase major blood vessels. Non-small cell lung cancer (NSCLC) with squamous cell differentiation is known for significant lung cavitations and centrally located tumours that may invade major blood vessels. Thus, the anatomic location and characteristics of tumour as well as the medical history should be carefully reviewed in the selection of subjects for treatment with cabozantinib;
- Recent or concurrent radiation to the thoracic cavity;
- Active peptic ulcer disease, inflammatory GI diseases including Crohn's disease and ulcerative colitis;
- Underlying medical conditions which affect normal haemostasis (e.g. deficiencies in clotting factors and/or platelet function, or thrombocytopenia);
- Concomitant medication with anticoagulants or other drugs which affect normal haemostasis;
- History of clinically significant haemoptysis, hematemesis, or haematuria.

The risk of haemorrhage in cabozantinib-treated subjects with brain metastases has not been thoroughly analysed. Though the incidence of CNS haemorrhage events in a study of subjects with GB was higher than observed in general population of subjects with cancer treated with cabozantinib, it is not clear how the risk of haemorrhage in GB translates to a risk of haemorrhage for subjects with brain metastases. Currently, brain metastases of carcinomas are not contraindications to the use of cabozantinib, but subjects with brain metastases should be monitored with a high index of suspicion if symptoms that could be due to a CNS haemorrhage occur.

Complete healing from radiation-induced side effects should have occurred before initiating cabozantinib treatment, and cabozantinib should be discontinued in subjects with serious and life-threatening bleeding events or recent haemoptysis ( $\geq 2.5$  mL of red blood).

## 4 VASCULAR DISORDERS

### Thromboembolic events

Thromboembolic events are frequent in cancer subjects due to procoagulant changes induced by the malignancy or anti-cancer therapy. Events of DVT and pulmonary embolism have been observed in clinical studies with cabozantinib, including fatal events. Subjects who develop a pulmonary embolism and/or DVT should have study treatment held until therapeutic anticoagulation is established. Refer to the individual protocol for guidance on anticoagulation medication use. Treatment with cabozantinib may be resumed in subjects with pulmonary embolism or DVT if it is determined that the event is uncomplicated and that the subject is deriving clinical benefit from cabozantinib treatment and that anticoagulation does not place them at a significant risk that outweighs the benefit of resuming study treatment per discretion of the Investigator and according to individual protocols. LMWHs are the preferred management agent for thrombotic events; Oral anticoagulants (including warfarin) are not allowed.

Arterial thrombotic events (e.g. TIA, MI) have been observed in studies with cabozantinib. Subjects should be evaluated for pre-existing risk factors for arterial thrombotic events such as diabetes mellitus, hyperlipidaemia, hypertension, coronary artery disease, history of tobacco use, and cardiac and/or thromboembolic events that occurred prior to initiation of study treatment. Further treatment with cabozantinib should be discontinued in subjects who develop an acute MI, cerebral infarction, or any other clinically significant arterial thromboembolic complication.

### Aneurysms and artery dissections

The use of VEGF pathway inhibitors in patients with or without hypertension may promote the formation of aneurysms and/or artery dissections. Before initiating cabozantinib, this risk should be carefully considered in patients with risk factors such as hypertension or history of aneurysm.

### Hypertension

Table A1. 2 provides treatment guidelines for hypertension deemed related to cabozantinib. Subjects with known hypertension should be optimally managed prior to entry into clinical trials with cabozantinib according to entry criteria of specific protocols. The subjects' BP should be monitored in a constant position visit to visit, either sitting or supine in a relaxed setting. Decisions to decrease or hold the dose of study treatment must be based on BP readings

taken by a medical professional and must be confirmed with a second measurement at least 5 minutes following the first measurement.

**Table A1. 2 Management of Hypertension Related to Cabozantinib**

Criteria for Dose Modifications	Treatment/Cabozantinib Dose Modification
Subjects NOT receiving optimised anti-hypertensive therapy	

>150 mm Hg (systolic)a and <160 mm Hg OR >100 mm Hg (diastolic) and <110 mm Hg
	
 
• Optimise antihypertensive medications by adding new or additional antihypertensive medications and/or increase dose of existing medications.
 
• Reduce study treatment by one dose level if optimal antihypertensive therapy (usually to include 3 agents) does not result in BP <150 mm Hg systolic or <100 mm Hg diastolic
 
• If subject is symptomatic interrupt study treatment
 

≥160 mm Hg (systolic) OR ≥110 mm Hg (diastolic)
	
 
• Reduce cabozantinib by one dose levelb or interrupt study treatment per Investigator's discretion
 
• Add new or additional anti-hypertensive medications and/or increase dose of existing medications and monitor subject closely for hypotension. If optimised antihypertensive therapy (usually to include 3 agents) does not result in BP <150 mm Hg systolic or <100 mm Hg diastolic, study treatment should be dose reduced further or interrupted
 
• Study treatment should be dose interrupted if upper limits of systolic BP (≥160 mm Hg) are sustained and not adequately manageable or if systolic BP is >180 mm Hg or diastolic BP >110 mm Hg, or if subject is symptomatic
 
• Re-start study treatment at the most tolerable dose and re-escalate only if BP falls to and is sustained at <150 mm Hg systolic and <100 mm Hg diastolic
 

Hypertensive emergency c	
 
• Discontinue study treatment
 

BP = Blood pressure.

a The Investigator may decide to initiate or adjust antihypertensive treatment at a lower threshold than systolic BP >150 or diastolic BP >100 based on their clinical judgment and assessment of the individual subject.

b Permitted dose levels are defined by individual protocols.

c Hypertensive emergency is defined as uncontrolled elevated BP with clinical evidence of progressive or impending end-organ damage (e.g. MI/ischaemia, intracranial haemorrhage, cerebral ischaemia, pulmonary oedema, encephalopathy, kidney damage).

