### ***6.2.2 Cabozantinib Dose Modifications, Interruptions and Discontinuation***

Subjects will be monitored for AEs from the time of signing informed consent until 30 days after the date of the last dose of cabozantinib. Any SAE that the Investigator believes to be related to cabozantinib or study procedures can be reported at any time after the last dose with no time limitation during the follow-up period. Subjects will be instructed to notify their physician immediately for any occurring AE and unscheduled safety visits are allowed at any time. Causality assessment of AEs should include at minimum confounding factors such as disease and concomitant medications. The severity of all AEs will be graded by the Investigator according to the CTCAE version 5.0.

The following should be taken into consideration in decisions regarding dose modifications (reductions or interruptions):

- As a general approach, all AEs should be managed with supportive care at the earliest signs of toxicity considered. Should this be ineffective, dose reductions or interruptions should be considered to prevent worsening of toxicity;
- The assigned dose for cabozantinib is 60 mg/day. Two reductions in dose levels of cabozantinib are permitted but these reductions must be incremental (see [Table 3](#));
- Dose modification criteria for cabozantinib are shown in [Table 4](#). Dose reductions and/or interruptions should be implemented for unacceptable toxicity. Doses may be modified at any time during the study;
- Dose modifications or interruptions may also occur in the setting of lower grade toxicity than that defined in [Table 4](#), if the Investigator feels it is in the interest of a subject's safety and will optimise drug tolerability;
- Interruption of cabozantinib treatment due to AEs may occur at any time per Investigator discretion. If study treatment is interrupted due to AEs for more than 6 weeks, cabozantinib should be discontinued;
- Dose interruptions for reason(s) other than AEs (e.g. surgical procedures) can be longer than 6 weeks but require Sponsor approval. The acceptable length of interruption will depend on agreement between Investigator and the Sponsor.

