**Table 3 Dose Reductions of Cabozantinib**

Assigned dose	First Dose Level Reduction	Second Dose Level Reduction
60 mg cabozantinib orally q.d.	40 mg cabozantinib orally q.d.	20 mg cabozantinib orally q.d.

Abbreviations: q.d. = Once daily

Cabozantinib should be discontinued if a dose of 20 mg q.d. (minimum dose) is not tolerated

Table 4 Dose Modifications of Cabozantinib for Treatment-related AEs

Common Terminology Criteria for Adverse Events (CTCAE) version 5.0 Grade	Recommended Guidelines for Management a
Grade 1 AEs	Add supportive care as indicated. Continue cabozantinib treatment at the current dose level if AE is manageable and tolerable.
Grade 2 AEs which are tolerable and are easily managed	Continue cabozantinib treatment at the current dose level with supportive care.
Grade 2 AEs which are intolerable and cannot be adequately managed	At the discretion of the Investigator, cabozantinib should be dose reduced or interrupted. Note: It is recommended that dose holds be as brief as possible.
Grade 3 AEs (except clinically non-relevant laboratory abnormalities)	Cabozantinib must be interrupted until the adverse reaction resolves to Grade $\leq 1$ . Note: It is recommended that dose holds be as brief as possible.
Grade 4 AEs (except clinically non-relevant laboratory abnormalities)	Subjects should have cabozantinib interrupted immediately. Discontinue cabozantinib unless the following criteria are met: 
 
• Subject is deriving clear clinical benefit as determined by the Investigator;
 
• Toxicity can be managed with a dose reduction following recovery to Grade 1 (or baseline) and optimal medical care.
 

Abbreviations: AE = Adverse event.

Note: The dose delay and modification criteria for specific medical conditions are provided in [Section 6.2.4](#). For reinstatement of cabozantinib after dose interruption, please see [Section 6.2.3](#).

a Dose adjustment is only needed if toxicity is considered to be related or has an unclear relationship to cabozantinib treatment.

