#### **6.2.4 Cabozantinib Warnings, Precautions and Guidelines for Management of Potential Adverse Events**

The side effect profile of cabozantinib includes, in descending order of frequency, diarrhoea, fatigue, decreased appetite, nausea, palmar-plantar erythrodysesthesia syndrome (PPES), vomiting, weight decreased, hypertension, constipation, dysphonia and asthenia (please refer to the Investigator's Brochure for additional details).

Subjects may also experience other medically important but less frequent AEs including arterial and venous thrombotic AEs (e.g. deep vein thrombosis (DVT), pulmonary embolism, TIA and MI), severe haemorrhagic events, proteinuria, wound healing complications, GI perforation, abscesses including intra-abdominal and pelvic abscess, GI and non-GI fistulae formation, osteonecrosis, and reversible posterior leukoencephalopathy syndrome (RPLS).

All AEs associated with laboratory abnormalities experienced by  $\geq 5\%$  of subjects treated with cabozantinib in descending order of frequency were anaemia, AST increased, ALT increased, hypothyroidism, hypokalaemia, hypomagnesaemia, thrombocytopenia, hypocalcaemia, hypophosphataemia, lactate dehydrogenase (LDH) increased, lipase increased, neutropenia, alkaline phosphatase (ALP) increased, hyponatraemia, and leukopenia.

All AEs should be managed with supportive care at the earliest signs of toxicity and dose reductions or study treatment interruptions should be considered. Dose reductions are recommended for events that, if persistent, could become serious or intolerable. A more detailed approach for management of potential AEs is provided in [Appendix 4](#).

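### Table A1.2 joins its two BP targets with 'or' in two dose bullets, leaving the row 1 reduction and the further row 2 step ambiguous when only one value stays high

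*Protocol*

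**What the plan says.** **The table (Protocol Appendix 4, Table A1.2).** It covers subjects not yet on optimised antihypertensive therapy.

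- Row 1 is entered on either value: ">150 mm Hg (systolic) a and <160 mm Hg OR >100 mm Hg (diastolic) and <110 mm Hg" (the single letter after the systolic term is a footnote mark). Its dose bullet reduces by one level if optimal therapy, usually three agents, "does not result in BP <150 mm Hg systolic or <100 mm Hg diastolic". Symptomatic subjects are interrupted.
- Row 2 is entered at systolic 160 or above, or diastolic 110 or above. Its first bullet directs a one-level reduction or an interruption, whatever the response to therapy. Its second bullet repeats the row 1 target wording as the condition for reducing further or interrupting. Its third bullet interrupts for sustained systolic of 160 or more that is not adequately manageable, for systolic above 180, for diastolic above 110, or for symptoms. Its last bullet restarts treatment at a tolerable dose and says to "re-escalate only if BP falls to and is sustained at <150 mm Hg systolic and <100 mm Hg diastolic".

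**Its standing.** The note under Table 4 (Section 6.2.2) says "The dose delay and modification criteria for specific medical conditions are provided in" Section 6.2.4, and that section refers on to Appendix 4. The text introducing Table A1.2 says "Decisions to decrease or hold the dose of study treatment must be based on BP readings", taken by a medical professional and confirmed by a second measurement.

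**General provisions.** On supportive care for adverse events, Section 6.2.2 says: "Should this be ineffective, dose reductions or interruptions should be considered to prevent worsening of toxicity". It also lets the investigator modify the dose at any time, including for toxicity of a lower grade than Table 4 defines. Section 6.2.4 adds: "Dose reductions are recommended for events that, if persistent, could become serious or intolerable"; Section 6.2.1 says the same.

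**The concern.** A patient enters row 1 because one of two values is too high. The dose bullet should then ask whether that value has come down. Read literally, it asks only whether at least one of the two is in range, and with an isolated elevation the other value was in range from the start. The condition for reducing the dose could then never be met while the pattern stays isolated.

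Two other places treat a single raised value as enough. The re-escalation bullet requires both values to be controlled. Exclusion criterion 6(b) in Section 4.2 defines uncontrolled hypertension by either a systolic or a diastolic limit.

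At stake is consistent dosing for a listed side effect. The table is the condition-specific rule that turns a BP reading into a dose action at about 50 sites in seven countries (Section 3.1). In the affected band, what it tells a site to do depends on how that site reads one conjunction.

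**Working it through.** The plan states no figure here, so there is none to reproduce. The check is logical.

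**Inputs (all from Table A1.2).** S is systolic and D is diastolic, in mm Hg, on optimised therapy.
- Row 1 entry: 150 < S < 160, or 100 < D < 110.
- Row 2 entry: S ≥ 160, or D ≥ 110.
- Target in both conditional bullets: S < 150 'or' D < 100.
- Re-escalation target: S < 150 'and' D < 100.

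**Dose-step condition (target not met).**
- Literal 'or': NOT(S < 150 OR D < 100) = (S ≥ 150 AND D ≥ 100).
- With 'and': NOT(S < 150 AND D < 100) = (S ≥ 150 OR D ≥ 100).

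**Row 1, asymptomatic, BP unchanged on optimised therapy.**

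| Pattern | Example | Reduce, literal 'or' | Reduce, 'and' |
|---|---|---|---|
| Isolated systolic, S 151–159 and D < 100 | 158/92 | no | yes |
| Isolated diastolic, D 101–109 and S < 150 | 145/108 | no | yes |
| Both high, S 151–159 and D 101–109 | 155/105 | yes | yes |
| Controlled after entry | 148/96 | no | no |

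The first three patterns are the main ways into row 1 but not the only ones. Readings of 155/100 and 150/105 also enter it, and they trigger reduction even on the literal reading, because neither value is below its target.

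**Row 2, asymptomatic.**

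| Entry → on therapy | Literal 'or' | What 'and' adds |
|---|---|---|
| 165/85 → 165/85 | first bullet; third bullet if sustained and not manageable | second-bullet further step |
| 140/112 → 140/112 | first bullet; third bullet (D > 110) | second-bullet further step |
| 140/110 → 140/110 | first bullet | second-bullet further step |
| 165/85 → 155/85 | first bullet only | second-bullet further step |

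**Grid check.** Whole mm Hg, S from 120 to 199 and D from 70 to 124, BP on therapy equal to entry BP, no symptoms, no hypertensive emergency.
- Row 1 isolated elevations: 9 × 30 systolic + 9 × 30 diastolic = 540 combinations. On the literal reading 540 of 540 have no dose instruction; with 'and', none lacks one.
- Row 2 isolated elevations: 40 × 30 + 15 × 30 = 1,650 combinations. Even on the literal reading, none lacks a dose instruction.

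These are combinations of readings, not patients. The documents give no frequency for any of these BP patterns.

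**The case against.** The strongest reply is that the table resolves its own ambiguity. 'Does not result in A or B' can be read as failing either target. That reading is natural here: a clinician who entered row 1 on a systolic of 158 would hardly count an already normal diastolic as control, and the re-escalation bullet shows that both values are meant. On this view only copy-editing remains. The point about intent stands. It does not remove the inconsistency, because a dose rule based on readings should not need its intent inferred from a bullet in another row.

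A second reply is that the general text already covers the patient. Section 6.2.2 allows dose changes at the investigator's discretion, and Sections 6.2.1 and 6.2.4 recommend reduction for persistent events that could become serious or intolerable. This also stands and limits the harm. Those provisions leave the decision to judgement, however, and set no BP threshold.

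A reader might infer that any persistent isolated elevation escapes dose reduction. The documents do not support that. Row 2's first bullet acts whatever the response, and its third acts on one value alone. Nor do they support the inference that patients in the row 1 band have no dose guidance at all. Table 4 acts by CTCAE grade, and since the documents do not give BP cut-offs for those grades, nothing can be said either way about whether it catches this band.

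**Conclusion.** The point holds as a minor wording error in a safety rule. It is confined to the row 1 reduction for an asymptomatic patient with a persistent isolated elevation (systolic 151–159 with diastolic below 100, or diastolic 101–109 with systolic below 150) and to the further step for a row 2 patient who settles in that band. On the literal reading the table calls for reduction in one of the three main row 1 patterns, against three of three with 'and'.

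This rests on taking the phrase literally and on BP not improving under optimised therapy. The safety consequence is small: the band is narrow, the safer reading is the natural one, and the investigator may reduce anyway. No patient count can be given, and no efficacy analysis or design figure changes.

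**What to change.** In the row 1 reduction bullet and the second row 2 bullet, replace 'or' with 'and', so that the target is systolic below 150 and diastolic below 100. Only the safer reading then remains, and it agrees with the rows' entry tests and the re-escalation bullet. The cost is one word in each of two bullets of Appendix 4, with no new data, visits or analyses.
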